6.2.4. Proportion of participants with $\geq 50\%$ reduction

Three separate repeated measures models (see section 4.7) will be used to model the probability

of a $\geq 50\%$ reduction in HB(4%), AHI(4%), and ODI(4%) values respectively. A logit link with binomial distribution will be employed. For each of the three endpoints, model based LS mean estimates will be provided for the following:

- odds ratios for a $\geq 50\%$ reduction for AD109 vs the other three treatments (placebo, R-oxibutynin, and atomoxetine) with 95% confidence intervals and respective p-values (for null hypothesis).

The proportion, with 95% CI, of participants with $\geq 50\%$ reduction in HB(4%), AHI(4%), and ODI(4%) will be presented by study treatment in the same table as the models.

6.3. Exploratory Efficacy Analyses

Descriptive statistics for the reported value and change from baseline by study treatment will be reported for sleep stages distribution and percentage of time in the various sleep stages (SE, WASO, NAW, SOL, Stage N1%, Stage N2%, Stage N3%, Stage R%). A 95% confidence interval will be included for the change from baseline.

Snoring index, arousal indices (respiratory and spontaneous), fraction of hypopneas (see below) and alternate measures of AHI, ODI, and HB (AHI[4%]: in NREM sleep, in REM sleep, AHI adjusted for position [see below]; AHI[3% or arousal]; HB[3% or arousal]; HB[Total]; ODI[3%]) and will have results provided similar to Section 6.1 (including the model of change from baseline and the descriptive statistics).

Additional clarifying details for the analysis of some of these endpoints is as follows:

- Fraction of hypopneas will be calculated by using the number of hypopneas divided by the total number of apneas plus hypopneas.
- AHI adjusted for position: An additional covariate of % time supine (%TS) will be added to the repeated measures model for AHI(4%).

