# 4 Study Design

## 4.1 Overall Design

Study APC-003 is a double-blind, placebo-controlled 4-period single dose crossover study designed to demonstrate the individual contribution of atomoxetine and R-oxybutynin to the efficacy of AD109.

Participants will undergo initial pre-screening to determine potential study eligibility. Patients selected for further screening should either have a previous history of OSA of a severity consistent with enrollment criteria or be at high risk (e.g. as assessed by STOP-Bang Questionnaire score). Only patients who meet all non-PSG enrollment criteria at Visit 1 are eligible for a screening PSG. A prior full-night PSG conducted by the study site within 6 months of Visit 1 that meets PSG enrollment criteria can take the place of a screening PSG.

[figure not shown]
Patients who meet all enrollment criteria will be randomized to receive the following experimental treatments, one treatment on each of 4 PSG night:

- Atomoxetine 75 mg + R-oxybutynin 2.5 mg (AD109)
- Atomoxetine 75 mg
- R-oxybutynin 2.5 mg
- Placebo

Dosing of the study treatment will occur immediately prior to lights out. Each morning following PSG exams in the crossover period the DSST will be administered.

Each PSG night is followed by a 1-week washout period. AE/SAE information is recorded at each study visit and by telephone contact with participants during each washout period and at the end of the final washout period. Overall study duration will be up to 14 weeks. A total of 58 participants will be enrolled. Participants who withdraw from the study will not be replaced.

Figure 1: Overview of Study Design

PSG = polysomnography.

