2.1.3. Exploratory Objective

The exploratory objectives are to evaluate the effects of AD109 compared to the other 3 study treatments on:

- Snoring index
- Sleep stages distribution and percentage of time in the various sleep stages
- Arousal index
- Fraction of hypopneas

- Alternative measures of AHI, ODI and HB

An additional exploratory objective is to evaluate the effects of AD109 compared to the other study treatments in the subgroup of participants meeting “moderate collapsibility” polysomnography (PSG) criteria at baseline (PSG-0).

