2.2.3. Exploratory Endpoints

The exploratory efficacy endpoints are as follows:

- PSG sleep and arousal parameters
 - Sleep stages distribution and percentage of time in the various sleep stages
 - Sleep Efficiency (SE)
 - Wake After Sleep Onset (WASO)
 - Number of Awakenings (NAW)
 - Sleep Onset Latency (SOL)
 - Percentage of total sleep time (TST) spent in sleep stage N1 (Stage N1%)
 - Percentage of TST spent in sleep stage N2 (Stage N2%)
 - Percentage of TST spent in sleep stage N3 (Stage N3%)
 - Percentage of TST spent in sleep stage R (Stage R%)
 - Snoring index
 - Arousal indices (respiratory and spontaneous)
 - Fraction of hypopneas

- Alternate measures of AHI, ODI and HB
 - AHI(4%) in non-rapid eye movement (NREM) sleep
 - AHI(4%) in rapid eye movement (REM) sleep
 - AHI(4%) adjusted for position
 - AHI(3% or arousal)
 - HB(3% or arousal)
 - HB(Total)
 - ODI(3%)
- Subgroup analyses of efficacy endpoints in participants meeting “moderate collapsibility” criteria (AHI[4%] 10 to <20, or AHI[4%] ≥20 if any one of the following are met: F_{hypopnea} of >90% OR mean oxygen desaturation of obstructive events of ≤4% OR F_{hypopnea} of 50 to 90% and mean oxygen desaturation of 4 to 8%) at baseline (PSG-0).

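### SAP 6.3 plans no interval for AD109 against placebo or the components on the sleep-stage and sleep-continuity variables; the only interval is for change from a pre-randomisation night.

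*SAP*

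**What the plan says.** SAP 2.1.3 introduces its list this way: "The exploratory objectives are to evaluate the effects of AD109 compared to the other 3 study treatments on". One entry is "Sleep stages distribution and percentage of time in the various sleep stages". SAP 2.2.3 then lists sleep efficiency (SE), wake after sleep onset (WASO), number of awakenings (NAW), sleep onset latency (SOL) and the four stage percentages (N1, N2, N3, R) as exploratory endpoints.

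SAP 6.3 divides the exploratory endpoints into two groups.

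- **Stages and continuity.** "Descriptive statistics for the reported value and change from baseline by study treatment will be reported for sleep stages distribution and percentage of time", with SE, WASO, NAW, SOL and the four stage percentages in the parenthesis that follows. The one interval is stated next: "A 95% confidence interval will be included for the change from baseline".
- **Snoring index, arousal indices, fraction of hypopneas and the alternate AHI, ODI and HB measures.** These are to have "results provided similar to Section 6.1 (including the model of change from baseline and the descriptive statistics"). SAP 6.1 supplies LS mean differences between AD109 and each of the other treatments, with 95% CIs and p-values.

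Under SAP 4.6, baseline is the last non-missing value before randomisation, which for PSG variables is the screening PSG. Protocol 4.1 allows a substitute: "A prior full-night PSG conducted by the study site within 6 months of Visit 1 that meets PSG enrollment criteria" may replace it.

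**The concern.** The design gives every participant a placebo night and a night on each component, so the natural estimate of a sleep effect is the within-participant difference between two randomised, blinded nights. For the eight stage and continuity variables, the plan attaches its only interval to a different contrast: a treated night minus an undosed night that was not randomised and always came first. Getting used to the laboratory, elapsed time and any change in conditions enter that contrast together with the drug effect.

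These variables help show whether AD109, or atomoxetine alone, disturbs sleep while hypoxic burden falls. Protocol 7.2 names sleep time and sleep stages among the effects to be monitored. Under SAP 6.3 as written, the placebo arm could show a sleep change whose interval excludes zero, and an AD109-placebo difference would be reported with no statement of its precision.

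**Working it through.** **Does another section supply the interval?**

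- SAP 4.5 speaks of three hypothesis tests in each group of endpoints, but its testing order covers only SAP 2.2.1 and 2.2.2.
- SAP 4.7 applies the repeated measures model to endpoints for which Section 6 calls on it. SAP 6.3 does not do so for the stage and continuity group.
- SAP 7.5 gives by-treatment descriptive statistics for total sleep time (TST) and a by-participant listing of PSG parameters.

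None gives a between-treatment interval for SE, WASO, NAW, SOL or the stage percentages.

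**Inputs.** The documents give no variance for any sleep variable, so the results are in units of s, the night-to-night SD within a participant. Assumptions: s is the same on every night and nights are independent. Completers: 58 × (1 − 0.20) = 46.4, taken as 46 (Protocol 8.1 and SAP 9 give 58 and a discontinuation rate below 20%). The stated sample size concerns HB only, and the point does not depend on it.

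**Half-width of a within-arm change from baseline.** The variance of the mean change is 2s²/46:

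t(0.975, 45) × s × √(2/46) = 2.014 × 0.2085 × s = 0.42s

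**Half-width of the AD109-minus-placebo difference.** The two mean changes share a baseline, so their covariance is s²/46. The variance of the difference is

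2s²/46 + 2s²/46 − 2 × s²/46 = 2s²/46

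The half-width is again 0.42s, so under these assumptions the randomised contrast is as precise as the one planned.

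**Can the two within-arm intervals be combined?** Not without the covariance, which is not reported. A reader who treats the two arms as independent would use 2.014 × √(4/46) × s = 0.59s, wider than the correct 0.42s.

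**Effect of a shift between the baseline night and the study nights.** Suppose there is no drug effect and a true mean shift of b. The chance that the placebo change interval excludes zero follows from the noncentral t distribution with 45 degrees of freedom and noncentrality b/(s√(2/46)):

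| True shift b | Probability that the placebo interval excludes zero |
|---|---|
| 0 | 5.0% |
| 0.1s | 7.6% |
| 0.2s | 15.5% |
| 0.3s | 29.1% |
| 0.5s | 65.0% |

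A shift common to all study nights cancels in AD109 minus placebo, so the interval for that difference keeps its 5% error rate.

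**The case against.** The strongest reply is that the endpoints are exploratory, that describing them by arm is a common and legitimate choice, and that a reader loses little. Much of this stands, and it rules out several stronger readings.

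- A reader might infer that the placebo night goes unused. It does not: values and changes are summarised for every treatment, and SAP 7.5 lists PSG data by participant. With complete data the shared baseline cancels when mean changes are subtracted, so the point difference can be recovered. Only the planned interval is missing.
- A reader might infer that sleep disruption gets no randomised contrast at all. The respiratory and spontaneous arousal indices get modelled contrasts under SAP 6.3, and next-morning DSST gets modelled ratios with CIs under SAP 7.4.
- A reader might infer that SAP 2.1.3 promises a comparison on all eight variables. It names sleep stages. SE, WASO, NAW and SOL enter through SAP 2.2.3 and the parenthesis in SAP 6.3, so the explicit mismatch concerns stages only.
- A reader might infer that a shift of 0.42s would make the interval exclude zero in every arm. That confuses an observed change with a true shift. Under the same assumptions, a true shift of 0.42s does so about half the time in a given arm, and in all four arms in about 20% of simulations.
- A reader might infer that treatments will be judged by whether their within-arm intervals overlap. No section plans that rule.

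The size of any shift is also unknown. The documents give no figure for laboratory adaptation. They do not say how many participants will use an earlier site PSG, or under what CPAP, medication or alcohol conditions it was recorded.

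What the reply does not answer is the uneven treatment within SAP 6.3. The snoring and arousal indices get the randomised contrast, while stages and continuity, from the same nights, do not.

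**Conclusion.** The point holds as a minor one. For SE, WASO, NAW, SOL and Stage N1, N2, N3 and R%, the plan gives no interval for the within-participant difference between AD109 and any comparator, although SAP 2.1.3 sets that comparison as an objective for sleep stages. The interval it does give cannot separate drug effect from a shift between the baseline night and the study nights. The 29% and 65% figures illustrate how easily such a shift could pass for an effect. They rest on 46 completers, equal and independent night-to-night variance, and assumed shifts of 0.3s and 0.5s; they do not predict that a shift of that size will occur. The reading of SAP 2.1.3 and 6.3 needs none of these assumptions. No primary or secondary conclusion is affected.

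**What to change.** In SAP 6.3, apply the Section 4.7 model to SE, WASO, NAW, SOL and Stage N1, N2, N3 and R%, and to TST alongside them. Report AD109 minus placebo, minus R-oxybutynin and minus atomoxetine with 95% CIs, labelled exploratory and unadjusted for multiplicity. Section 4.7 defaults to a Gaussian distribution with identity link, so name a transformation or a suitable distribution for the variables that may be skewed or are counts (SOL, WASO, NAW). The change-from-baseline interval can stay as a descriptive column.

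The cost is a short addition to the text and further runs of a model already being programmed. It needs no new data and uses no alpha, because these endpoints lie outside the fixed sequence in SAP 4.5. The drawback is 8 × 3 = 24 more unadjusted contrasts, or 27 with TST, which the label should make plain. If the sponsor prefers to leave the analysis descriptive, rewording the sleep-stage item in SAP 2.1.3 as descriptive would remove the mismatch, but the treatment differences would still lack intervals.

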7. SAFETY ANALYSIS

Safety assessments will include measurement of adverse events (AEs) and serious AEs (SAEs).

The analyses will be descriptive and will be based on the Safety Set. The safety assessments will be summarized by the treatment the participant actually received within each period.

7.1. Extent of Exposure

The number and percentage of participants receiving study treatment will be summarized by study treatment and overall. A by-patient listing will be provided.

7.2. Adverse Events

An AE is any untoward medical occurrence in a participant or clinical study participant, temporally associated with the use of a study treatment, whether or not considered related to the medicinal product.

An AE can therefore be any unfavorable and unintended sign (including an abnormal laboratory finding), symptom, or disease (new or exacerbated) temporally associated with the use of a study treatment.

7.2.1. Treatment-emergent Adverse Events

A treatment-emergent adverse event (TEAE) is defined as any event not present prior to exposure of study drug or an event already present that worsens in either severity or frequency following exposure. Each TEAE is assigned to the most recent study treatment administered on or before the TEAE's date of onset.

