## 1.2 Schedule of Activities (SoA)

 Table 1
 Schedule of Activities

	Screening		4-Way Crossover Period Visit 3-6						End of Study Evaluation 		
Procedures	Daytime V1	PSG V2	PSG V3	Wash- out 	PSG V4	Wash- out	PSG V5	Wash- out	PSG V6	Wash- out	
Trial Day (Visit Window)	Up to 4 w	veeks				Up to 8	weeks				2 weeks post V6 ± 3 days
Informed consent	X										
Non-PSG enrollment criteria	X										
Demography	X										
ESS	X										
Physical exam	X										
Medical history	X										
Clinical laboratory test	X										
Pregnancy test 	X										
12 Lead ECG	X										
PSG Exam		$X^4$	X		X		X		X		
Randomization 			X								
Administration of study treatment 			X		X		X		X		
DSST 			X		X		X		X		
Vital signs 	X	X	X		X		X		X		
AE/SAE monitoring			X	X	X	X	X	X	X	X	X
Prior/concomitant medication monitoring	X	X	X	X	X	X	X	X	X	X	X

Abbreviations: AE = adverse event; DSST = Digit Symbol Substitution Test; ECG = electrocardiogram; ESS = Epworth Sleepiness Scale; PSG = polysomnography; SAE = serious adverse event; WOCBP = women of childbearing potential.

<sup>1 Can be conducted remotely. For patients enrolling in Study APC-003-OLE, can be conducted concurrently with first visit of Study APC-003-OLE.

<sup>2 Each washout period is a minimum of 7 days

<sup>3 WOCBP only

<sup>4 A PSG conducted by the study site within 6 months that meets PSG enrollment criteria can take the place of a screening PSG and V2

<sup>5 Randomization occurs when participant meets enrollment criteria up to the time of the first crossover period

<sup>6 Study medication administered immediately before lights out

<sup>7 Administer at similar time after awakening after each crossover PSG, approximately 1 hour after awakening

<sup>8 Vital signs include the following: seated blood pressure, pulse, respiratory rate; vital signs on PSG nights taken after admission to PSG lab

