## 7.1.1 Polysomnography

- Methods: Standard overnight PSG recording and data interpretation will be performed in accordance with the American Academy of Sleep Medicine (AASM) scoring manual.
   Participants will be instrumented with standard PSG electrodes. Time of lights out will be established according to the participants' habitual schedule and kept constant across the PSG study nights. The participants will be given 8 hours of time-in bed.
- Scoring: All PSG studies (including screening PSG) will be scored by centralized PSG technologists, blinded to treatment assignment. Scoring will be conducted according to the American Academy of Sleep Medicine manual scoring criteria.

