3.2.3. Dosing Schedule

There are 4 randomized crossover PSG nights. Each PSG night is followed by a 1-week washout period. Dosing of the study treatment will occur immediately prior to lights out.

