All occurrences of all AEs will be listed for each participant, grouped by treatment. The listing will contain the following information: treatment sequence, treatment, verbatim term, SOC, PT, intensity, relationship to study medication, date and day of onset, date and day of resolution, treatment given to treat the adverse event, action taken, the outcome, whether the event was an SAE, whether it led to withdrawal. Listings will be sorted by treatment sequence, participant identification number, onset date, SOC, and PT. If onset year is non-missing but month and/or date is missing, then the day of the most recent study drug dose will be imputed as onset date.

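### SAP 7.2.1 assigns TEAEs by calendar date although dosing is at bedtime, so a TEAE that starts on the V4, V5 or V6 dosing date before that night's dose is charged to a treatment not yet taken

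*SAP*

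**What the plan says.** SAP 7.2.1 defines a TEAE as "any event not present prior to exposure of study drug or an event already present that worsens in either severity or frequency following exposure". It then gives the allocation rule: "Each TEAE is assigned to the most recent study treatment administered on or before the TEAE's date of onset". The comparison is between dates, and the dosing date itself counts.

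Both documents put the dose at the end of the day. SAP 3.2.3 says "Dosing of the study treatment will occur immediately prior to lights out", and a footnote to the Schedule of Activities (Protocol 1.2) says "Study medication administered immediately before lights out". Protocol 7.1.1 gives no clock time: "Time of lights out will be established according to the participants' habitual schedule and kept constant across the PSG study nights".

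Adverse events can be noted on a dosing date before the dose. Protocol 4.1 says "AE/SAE information is recorded at each study visit and by telephone contact with participants during each washout period", and another Schedule of Activities footnote has "vital signs on PSG nights taken after admission to PSG lab".

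The AE listing described in SAP 7.2.5 carries the date and study day of onset, but no clock time and no marker for before or after the dose. For incomplete onset dates with a known year, the same section says "then the day of the most recent study drug dose will be imputed as onset date". Neither document has a rule for an event that starts on a dosing date before the dose.

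**The concern.** The allocation rule works in whole days, but exposure changes late in the evening. On the V4, V5 and V6 dates the participant spends nearly the whole day after the previous treatment and before the next. The rule nevertheless treats that whole day as belonging to the next one.

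All the by-treatment TEAE summaries in SAP 7.2.5 depend on this allocation, including those by intensity, relationship and discontinuation. They are the main safety output of a four-treatment crossover. An event charged to a drug not yet taken is wrong in itself. It can also contradict the investigator's causality assessment, which SAP 7.2.3 says should weigh timing relative to dosing.

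**Working it through.** The documents state no figure for this, so there is none to reproduce. The check is a worked case followed by a sizing.

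**Worked case.** Treatment X is given at 22:00 on Day 1 and treatment Y at 22:00 on Day 8. A headache starts at 10:00 on Day 8. Its onset date is Day 8, and Y was given on Day 8, so the rule assigns it to Y. Only X had been taken. Three neighbouring cases come out differently:

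- Headache at 23:00 on Day 8: assigned to Y, correctly.
- Headache that began on Day 6 and is reported at admission on Day 8: onset date Day 6, assigned to X, correctly.
- Headache at 10:00 on Day 1, before the first dose: not a TEAE under the definition unless it later worsens. A date alone cannot separate it from an event that starts after the dose on Day 1.

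**Inputs**

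- Between-dose interval: at least 7 days (Schedule of Activities footnote). The crossover may last up to 8 weeks. If four washouts fill it, 8 × 7 / 4 = 14 days each. Both 7 and 14 are used.
- Follow-up after the last dose: 14 days (End of Study evaluation 2 weeks after V6).
- Dose clock time: not given. Assumed 21:00 to 24:00, with 00:30 as a variant.
- Affected dosing dates: three (V4, V5, V6).

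**Share of one between-dose interval** = hours from midnight to dose / (24 × days between doses)

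| Dose time (assumed) | 7 days (168 h) | 14 days (336 h) |
|---|---|---|
| 21:00 | 21/168 = 12.5% | 21/336 = 6.25% |
| 22:00 | 22/168 = 13.1% | 22/336 = 6.5% |
| 23:00 | 23/168 = 13.7% | 23/336 = 6.8% |
| 24:00 | 24/168 = 14.3% | 24/336 = 7.1% |
| 00:30 | 0.5/168 = 0.3% | 0.5/336 = 0.15% |

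The last row supposes that the dose is recorded under its actual date, after midnight.

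**Share of evenly occurring events over the study**, from first dose to 14 days after the last = 3 × hours to dose / total hours

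- 7-day spacing: total (3 × 7 + 14) × 24 = 840 h. At 22:00, 66/840 = 7.9%; from 21:00 to 24:00, 63/840 = 7.5% to 72/840 = 8.6%.
- 14-day spacing: total (3 × 14 + 14) × 24 = 1344 h. At 22:00, 66/1344 = 4.9%; from 21:00 to 24:00, 63/1344 = 4.7% to 72/1344 = 5.4%.

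A simulation of uniformly timed events with a 22:00 dose, comparing the written rule with a date-and-time rule, gave 7.8% and 4.9%.

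**Direction.** Each misassigned event moves one period forward. SAP 3.2.1 uses all 24 sequences, so each treatment stands in each period in 6 of them. What a treatment gains and loses should roughly cancel for background events.

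**The case against.** The best defence is that the word on is there for a reason. With bedtime dosing, a genuine early effect can begin before midnight on the dosing date. If only dates are available, a strict before rule would send that event to the previous treatment, which is arguably the worse error. This stands, and it is why the present convention should remain the fallback when timing is unknown.

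The second defence concerns size. Each treatment is a single dose, so acute effects are expected that night and the next day, and the rule handles those properly. The affected window is the last day of an interval of at least 7 days, when most events will be background. The safety analyses are descriptive (SAP 7), and the listing shows sequence, treatment and onset date, so dosing-date events can be found and reviewed. All of this stands and limits the consequence. It does not make the allocation right.

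Four stronger readings are tempting, and the documents do not support them:

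- A reader might infer that whatever is found at PSG admission is misassigned. Onset date governs, not detection. An abnormal vital sign is an AE only if the investigator judges it clinically significant (Protocol Appendix 3), so admission checks do not imply a steady stream of such events.
- A reader might take 13% as the share of TEAEs affected. It is a share of time within one interval, at the minimum spacing and an assumed 22:00 dose.
- A reader might infer bias for or against AD109. The balanced set of sequences argues against that.
- A reader might conclude that onset time is not collected. SAP 7.2.5 describes a listing, and the eCRF is not among the documents.

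**Conclusion.** The point holds for TEAEs with onset dated to the V4, V5 or V6 dosing date that began before that night's dose. The stated rule gives a wrong answer for them, and nothing else in either document repairs it. At V3 the definition excludes pre-dose events, but the dates alone cannot apply it.

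The size is modest: 12.5–14.3% of a 7-day interval or about 6.2–7.1% of a 14-day one, and about 5–8% of background events study-wide with a 22:00 dose. This rests on dosing before midnight and, for the study-wide figure, on events spread evenly over time. Dosing after midnight makes it negligible. The effect is some blurring of descriptive tables, roughly even across treatments. Efficacy tests, type I error and power are untouched.

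The partial-date rule in SAP 7.2.5 is a lesser matter. It does not say what the dose is most recent relative to, and it can be read sensibly. As written, though, nothing stops an imputed onset from contradicting a known month or a recorded resolution date.

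**What to change.** Amend SAP 7.2.1 for events with onset on a dosing date:

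- Assign to that night's treatment only if onset is after the dose, judged by onset time against dose time or by a before/after-dose flag.
- Otherwise assign to the previous treatment, or at V3 classify as pre-treatment.
- If timing is unknown, keep the current convention and flag the event in the AE listing.

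In SAP 7.2.5, add that an imputed onset date must fit the known year and month and must not fall after resolution.

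The cost is a few lines of SAP text and, if onset time is not already collected, one eCRF item. Some timings will stay unknown, particularly for events already recorded or reported by telephone during washout, so the fallback will be needed.
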